11.3 Power and Sample Size

11.3.1 Prior studies suggest an average proportion of 0.50 of patients who are free from in-field progression at 2 years following standard radiotherapy alone. ^{4,9} Based on prior reports of dose escalated hypofractionated radiotherapy and our institutional experience using a similar dose fractionation scheme, we hypothesize that HRT will improve 2 year freedom from in-field progression from this 50% to 75%. ^{1,2,22} With a sample size of n=25, we will have 80% power to detect this increase, assuming a one-tailed α of 0.05. We anticipate that approximately 10% -15% of patients recruited will not provide data on our primary outcome at 2 years, so we anticipate recruiting n=30 patients total to allow us to have a total n of 25 for our primary analysis.

11.4 Estimated Accrual Rate

11.4.1 Based on review of recent case volume at WFBMC, we estimate one accrual per month across all sites, or 12 patients per year.

11.5 Estimated Study Length

11.5.1 Based on the estimated accrual rate, we anticipate a 2.5 year (29-31 months) duration of accrual.

11.6 Interim Analysis Plan

No formal interim analysis is planned; however, if 5 patients develop Grade 4 or 5 bronchial fistula, bronchopulmonary hemorrhage, esophageal fistula, hemorrhage or perforation as defined by CTCAE version 5.0, the study will be halted. Patients who have known in-field progression of disease or new or

progressive disease involving the structure that develops the Grade 4 or 5 toxicity prior to toxicity development will not be counted.

References

Appendix A – Eligibility Checklist

IRB Protocol No. WFBCCC Protocol No.62220			
Study Title: A Single Arm Phase II Study of Hy	pofractionated	Radiotherapy A	llone in Locally Advanced NSCLC Patients
who Decline or are Ineligible for Surgery or Che	emotherapy		•
Principal Investigator [name]			
Inclusion Criteria	Criteria is	Criteria is	Source Used to Confirm *
(as outlined in study protocol)	met	NOT met	(Please document dates and lab results)
Histological confirmation of non-small cell lung	_	_	
cancer by either biopsy or cytology			
AJCC 8th Edition Stage II-III or ultracentral			
Stage IB NSCLC as determined by PET/CT and			
MRI Brain			
ECOG Performance Status of 0-3			
Patient is not eligible for or has declined			
surgical resection or SBRT as determined by the			
treating physician			
Patient is not eligible for or has declined			
concurrent chemotherapy as determined by the			
treating physician			
While we expect it to be an uncommon event,			
sequential use of systemic therapy after			
completion of RT is permissible if the patient's			
status improves such that they become eligible			
for such therapies, per the discretion of a			
multidisciplinary tumor board.			
Negative serum or urine pregnancy test within 2			
weeks of the date of enrollment			
for women of child-bearing potential			
Ability to understand and the willingness to sign			
an IRB-approved informed consent document			
(either directly or via a legally authorized			
representative)			
Follows Cottons	Criteria	Coltania in	C U14- C \$
Exclusion Criteria	NOT	Criteria is	Source Used to Confirm *
(as outlined in study protocol)	present	present	(Please document dates and lab results)
History of previous thoracic radiotherapy with			
the exception of prior radiotherapy for breast			
cancer without overlap of the fields with the			
cancer to be treated			
Prior systemic therapy or surgery for the study			
cancer			
Prior malignancy within the past two years			
except for non-melanoma skin cancer, prostate			
cancer, or any in-situ malignancy			
Receipt of anti-angiogenic therapy within 6		-	
months of enrollment			
Pregnant women are excluded from this study			
because radiation therapy has known potential			
for teratogenic or abortifacient effects			

This subject is	\square eligible / \square ineligible	for participation in this study.
OnCore Assigne	ed PID:	
Signature of rese	earch professional confirmir	ng eligibility:
Date: /	/	
Signature of Tre	ating Physician:	
Date:/	/	
Signature of Prin	ncipal Investigator**:	
Date: /	/	

^{*} Examples of source documents include clinic note, pathology report, laboratory results, etc. When listing the source, specifically state which document in the medical record was used to assess eligibility. Also include the date on the document. Example: "Pathology report, 01/01/14" or "Clinic note, 01/01/14"

^{**}Principal Investigator signature can be obtained following registration if needed

Appendix B - Protocol Registration Form

DEMOGRAPHICS	
Patient: Last Name:	First Name:
MRN:	DOB (mm/dd/yy): / //
ZIPCODE:	
SEX: □ Male □ Female	Ethnicity (choose one):
	□Non-Hispanic
Race (choose all that apply): □ WHITE □BLA	ACK □ ASIAN
□ PACIFIC ISLANDE	R □ NATIVE AMERICAN
Height: inches	Weight:lbs.(actual)
Surface Area: m ²	
Primary Diagnosis:	
Date of Diagnosis: //	
Performance Status: □ ECOG	
DD OTO GOL DIFFORMATION	
PROTOCOL INFORMATION	
Date of Registration:	//
MD Name (last):	
Date protocol treatment started:	//
Informed written consent:	□ YES □ NO
(consent must be signed prior to registration)	
Date Consent Signed:	//
PID # (to be assigned by OnCore):	

Protocol Registrar can be contact by calling [contact] between 8:30 AM and 4:00 PM, Monday – Friday.

Compete the eligibility checklist in WISER and then give the completed Eligibility Checklist and Protocol Registration Form must be hand delivered, faxed or e-mailed to the registrar at [contact] or [contact], respectively.

Appendix C - Race & Ethnicity Verification Form

Thank you so much for helping us to verify your race and ethnicity to ensure the quality of our information. As a brief reminder, the information you provide today will be kept confidential.

1. Are you:
Hispanic or Latino/a
Not Hispanic or Latino/a
Not Hispanic of Latino/a
2. What is your race? One or more categories may be selected. White or Caucasian Black or African American American Indian or Alaskan Native Asian Native Hawaiian or Other Pacific Islander Other, Please Specify:
Internal use only:
Name: MRN#:
Was the self-reported race and ethnicity of the participant verified at the time of consent? Yes No
Was a discrepancy found? Yes No \[\]
If yes, please provide what is currently indicated in the EMR:
Ethnicity: Race:
Additional comments:

Appendix D Safety and Toxicity Review Committee (STRC) Serious Adverse Event (SAE) Notification SOP

Data and Safety Monitoring	Date: 02/11/2021
Committee (DSMC) Serious Adverse	
Event (SAE) Notification SOP	

Mandatory DSMC SAE Reporting Requirements in WISER

This document describes reporting requirements of adverse events from WFBCCC Investigator Initiated interventional trials to the Data and Safety Monitoring Committee (DSMC). A trial is considered a WFBCCC Investigator Initiated interventional trial if the following criteria are met:

- 1) The Principal Investigator (PI) of the trial is a member of a department at the Wake Forest University Baptist Medical Center.
- 2) WFBCCC is considered as the primary contributor to the design, implementation and/or monitoring of the trial.
- 3) The trial is designated as "Interventional" using the Clinical Research Categories definitions provided by the NCI in the Data Table 4 documentation.

(https://cancercenters.cancer.gov/GrantsFunding/DataGuide#dt4)

There are two distinct types of WFBCCC Investigator Initiated interventional trials based on where patient enrollment occurs. These include:

- 1) Local WFBCCC Investigator Initiated interventional trials defined as trials where all patients are enrolled from one of the WFBCCC sites. These include the main outpatient Cancer Center clinics (located in Winston-Salem) as well as WFBCCC affiliate sites located in Bermuda Run (Davie Medical Center), Clemmons, Lexington, High Point, or Wilkesboro.
- 2) Multi-Center WFBCCC Investigator Initiated interventional trials defined as trials where patients are enrolled from other sites in addition to WFBCCC sites.

 There are three types of trials that are included in this category:
 - a. Trials sponsored by the NCI Community Oncology Research Program
 (NCORP) that are conducted at multiple sites where the PI is a member of a
 department at the Wake Forest University Baptist Medical Center.
 - b. Trials sponsored by Industry that are conducted at multiple sites and the PI is a member of a department at the Wake Forest University Baptist Medical Center.
 - c. Trials sponsored by WFBCCC that are conducted at multiple sites and the PI is a member of a department at the Wake Forest University Baptist Medical Center.

All Adverse Events (AEs) and Serious Adverse Events (SAEs) that occur on any patients enrolled on WFBCCC Investigator Initiated Interventional trials must be entered into the WISER system. The only exception to this requirement is for patients enrolled on NCORP trials at non- WFBCCC sites. AEs and SAEs for NCORP patients enrolled at WFBCCC sites must be entered into the WISER system. Once these AEs and SAEs are entered in WISER, certain actions must be taken regarding the reporting of specific Adverse Events to the DSMC.

All Adverse Events that occur during protocol intervention (defined below) and are coded as either 1) unexpected grade 4, 2) unplanned inpatient hospitalization > 24 hours (regardless of grade), or grade 5 (death) must be reported to the DSMC using the using the SAE console in WISER.

A research nurse or clinical research coordinator when made aware that an adverse event meets one of the above criteria has occurred on a WFBCCC Investigator Initiated interventional trial, is responsible for informing a clinical member of the DSMC by phone (or in-person) about the adverse event. The nurse/coordinator should contact the treating physician prior to calling the DSMC clinical member to obtain all details of the SAE, as well as all associated toxicities to be recorded along with the SAE. In addition, this nurse or coordinator is responsible for entering the adverse event information into the SAE console in WISER. Once the adverse event has been entered into the SAE console an email informing the entire DSMC will be generated.

THESE REPORTING REQUIREMENTS APPLY TO any staff member on the study team for a WFBCCC Institutional Interventional trial. Ultimately, the protocol PI has the primary responsibility for AE identification, documentation, grading and assignment of attribution to the investigational agent/intervention. However, when an AE event as described above is observed, it is the responsibility of the person who observed the event to be sure that it is reported to the DSMC.

What is considered during protocol intervention?

During protocol intervention is considered to be the time period while a patient is on study treatment or during the time period within 30 days of last study treatment (even if patient begins a new (non-study) treatment during the 30 days). This window of 30 days should be the standard window to be used in all protocols unless a specific scientific rationale is presented to suggest that a shorter window can be used to identify events. If it is a trial sponsored by Industry and the sponsor requires a longer window for monitoring of SAEs, then the longer window of time specified by the sponsor should be followed.

What is considered as an Unexpected Grade 4 event?

Any grade 4 event that was not specifically listed as an expected adverse event in the protocol should be considered as unexpected. A grade 4 adverse event can be considered to be unexpected if it is an event that would not be expected based on the treatment being received or if it is unexpected based on the health of the patient. In either case, if there is

any uncertainty about whether a grade 4 adverse event is expected or unexpected it should be reported to DSMC.

DSMC notification responsibilities of the person (e.g., nurse) handling the reporting/documenting of the SAE in WISER:

- 1. Make a phone call (or speak in person) to the appropriate clinical member of the DSMC according to the schedule as listed below (page if necessary).
- 2. Enter a new SAE into the SAE module that is located in the Subject>> CRA Console inWISER WITHIN 24 HOURS of first knowledge of the event. Information can be entered and saved, but the DSMC members will not be notified until a date is entered into the DSMC Notification Date Field. This will ensure that all persons that need to be made aware of the event (i.e., PI, study team members and DSMC members) will be notified; remember to file a copy of the confirmation.
- 3. Document that the appropriate person(s) on the DSMC has been contacted. Indicate the name of the DSMC clinician that was contacted and the date and time contacted in the Event Narrative field in the SAE console of the particular subject.
- 4. Document whether or not the protocol should be suspended based on the discussion with the DSMC clinician. This is the major function of the email notification. Enter whether the protocol should be suspended in the Event Narrative Field.
- 5. Follow up/update the clinical member(s) of DSMC regarding any new developments or information obtained during the course of the SAE investigation and reporting process.

Elements needed to complete the SAE form in the Subject Console in WISER (see Screen Shot 3):

- Event Date
- 2. Reported Date
- 3. Reported by
- 4. If Grade 5, enter Death Date
- 5. If Grade 5, enter Death occurred: within 30 days
- 6. Event Narrative: Brief description (include brief clinical history relevant to this event, including therapies believed related to event). Begin narrative with the DSMC clinician who was notified and Date/Time notified. In addition, state attribution by DSMC clinician as either "Unrelated", "Unlikely", "Possibly", "Probably", or "Definitely". Always include the following here:
 - i. DSMC clinician name, date/time contacted and comments
 - ii. Date of last dose before the event
 - iii. Is suspension of the protocol needed? Y/N
- 7. Treating Physician comments
- 8. PI comments, if available
- 9. Protocol Attribution after discussion with DSMC clinician
- 10. Outcome (Fatal/Died, Intervention for AE Continues, Migrated AE, Not Recovered/Not Resolved, Recovered/Resolved with Sequelae, Recovered/Resolved without Sequelae, Recovering and Resolving)

- 11. Consent form Change Required? Y/N
- 12. SAE Classification *This is required in order for the email notification to be sent*
- 13. Adverse Event Details Enter all details for each AE associated with the SAE.
 - a. Course start date
 - b. Category
 - c. AE Detail
 - d. Comments
 - e. Grade/Severity
 - f. Unexpected Y/N
 - g. DLT Y/N
 - h. Attributions
 - i. Action
 - j. Therapy
 - k. Click ADD to attach the AE Detail to the SAE.
- 14. Enter Date Notified DSMC -- *This is required for the email notification to be sent*

It is the responsibility of the DSMC clinician to review all reported events, evaluate the events as they are reported; and communicate a response to the Investigator, event reporter and the members of DSMC. The review will include but not be limited to the information reported; there may be times when additional information is needed in order for an assessment to be made and further communication directly with the investigator may be warranted. DSMC reserves the right to disagree with the Investigator's assessment. If DSMC does not agree with the Investigator, DSMC reserves the right to suspend the trial pending further investigation. If there is any immediate danger or harm that could be present for a future patient based on the information provided in the DSMC report then an immediate suspension of enrollment shouldbe considered.

AMENDMENTS TO PREVIOUS REPORTS

If all pertinent information is unavailable with the initial submission, once the additional information is available **do not submit a new report**. Rather, go to the original email that was sent to the DSMC and using that email "reply to all". Entitle this new email "**Amendment** for (list date of event and patient ID)" this will avoid duplications of the same event. List the additional information being reported. This information needs to be entered into WISER as well. To do this, go to the Subject console and click SAEs on the left column. Click on the appropriate SAE number that needs updating. Then click Update. This will allow additional information to be added.

Acronyms

AE – Adverse Event

DSMC-Data and Safety Monitoring Committee

SAE-Serious Adverse Event

WFBCCC – Wake Forest Baptist Comprehensive Cancer Center

NCI-National Cancer Institute

WISER –Wake Integrated Solution for Enterprise Research

Screen Shots:

[figure not shown]
The following screen shots come from the SAE Console within the Subject Console in WISER.

[figure not shown]
Screen Shot 2:

Screen Shot 3:

Screen Shot 4:

Appendix E: BED Calculations for Dose Levels and Constraints

$$BED = d(n)(1 + d/(\alpha/\beta))$$

- Where:
 - BED = Biologic Effective Dose at a given alpha/beta ratio
 - d = dose per fraction
 - n = number of fractions
 - α/β = alpha/beta ratio

$$EQD2 = BED/(1 + (2/\alpha/\beta))$$

- Where:
 - EQD2 = Equivalent dose in 2 Gy fractions

BED and EQD2 Calculations									
Parameter	Total Dose (Gy)	Dose per fraction (Gy)	Number of Fractions	BED ₁₀ (tumor)	BED ₃ (normal tissue)	EQD2 ₁₀ (tumor)	EQD2 ₃ (normal tissue)		
Standard Therapy	60	2	30	72	100	60	60		
Prior Institutional HRT	70.2	2.7	26	89.15	133.38	74.3	80.03		
Prior HRT with Low Dose Cisplatin	66	2.75	66	84.15	126.5	70.13	75.9		
High Dose PTV	70	2.8	25	89.6	135.33	74.67	81.2		
High Dose PTV (bronchial invasion)	67.5	2.7	25	85.73	128.25	71.44	76.95		
Low Dose PTV	57.5	2.3	25	70.72	101.58	58.94	60.95		
Volumetric PBT Constraint	66.25	2.65	25	83.81	124.77	69.84	74.86		
Brachial Plexus Constraint*	60	2.4	25	74.4	132	62	66		

^{*} α/β of 2 used for normal tissue calculations for nervous system

Appendix G - Follow-up Form

Study Number: 62220 PID:
Investigator: [name] M.D. Date:/
Instructions: Complete this form to follow-up with patients for adverse events.
Name of Person Competing form
Did the subject have any adverse events in the last 30 days? Yes No If yes, please describe nature and grade of AE (Note*: If an SAE occurs in this period, report the event as required in Appendix D):
Was the subject removed from the study by the PI? Yes No
Did the subject withdraw from the study? Yes No
Did the subject complete the full course of SBRT and take the study drug? Yes No

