5.2 Secondary Outcomes

- 5.2.1 Toxicities will be evaluated per CTCAE Version 5.0 one month following completion of therapy and then every 3 months thereafter until 25 months from completion of radiation therapy.
- 5.2.2 Patterns of progression will be defined as follows: Local progression will be defined as in field progression (see Section 5.1.1); regional progression will be defined as any new regional lymphadenopathy in the hilum or mediastinum that was not included in the gross tumor volume (GTV); distant progression will be defined as any radiographic or pathologic evidence of disease outside the primary tumor and regional lymph nodes, including subsequent pulmonary parenchymal lesions. Progression-free survival will be evaluated by considering the time from registration to progression of disease or death; those who do not experience either outcome will be censored at date of last visit. Overall survival will be evaluated by considering the time from registration to death from any cause; those who do not die will be censored at date of last visit. Progression will be assessed through CT scans administered immediately following treatment and then every 3 months after that, out to 25 months.

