6.0 Treatment Plan

6.1 Study-Related Activities

Activity	Pre- Study ^a	Prior to First Fraction of RT	At Each Weekly Treatment Visit on RT	1 month after RT completion	Every 3 months after 1 month post-RT scan until 25 months after RT ¹
Informed consent	X				
Demographics	X				
Medical history	X			X	X
Concurrent meds	X				
Physical exam	X			X	X
Vital signs ^g	X			X	X
Height ^d , Weight, ^g	X			X	X
Performance Status ^g	X		X	X	X
Tumor measurements ^e	X			X	X
B-HCG ^b	X				
FDG PET/CT Skull Base to Mid Thigh ^j	X				
MRI Brain with contrasti	X				
CT Chest/Abdomen ^c				X	X
Adverse event evaluation ^f Mandatory target coverage/dose constraint	X	X	X	X	X
compliance ^k				: 121:	

^a Pre-study requirements listed in table must be completed within 12 weeks prior to registration.

^b Serum or urine pregnancy test (women of childbearing potential). This must be completed within one week prior to initiation of radiotherapy for women of childbearing potential. For our purposes postmenopausal women are defined as women over the age of 45 years old with at least 12 months from their date of last menstruation.

^c CT Chest/Abdomen will be with contrast unless the patient has a documented contraindication to IV CT contrast (ie inadequate renal function or anaphylaxis). The scan must include the entire bilateral lungs, liver, and bilateral adrenal glands. CT Chest/Abdomen/Pelvis is also acceptable.

^d Height measured at pre-study only

e See Appendix Q

f See Appendices F and G

g See Appendix L

^h See Appendix C

¹ If MRI is contraindicated, CT Head with contrast is also acceptable.

^j National guidelines indicates a PET scan is good for 3 months (12 weeks).

^k See Appendix N

¹For all follow-up imaging and clinic follow-up time points above, a flexibility window of +/- 8 weeks is allowed.

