11.2 Analysis of Secondary Objective

- 11.2.1 We will compute the proportion of the sample developing any toxicity of grade 2 or higher over the 25 months, and construct a corresponding 95% confidence interval.
- 11.2.2 We will compute proportions of patients who have experienced local progression by 13 months (1 year following first post-radiotherapy scan) and by 25 months (2 years following first post-radiotherapy scan), and will also compute the same two proportions considering regional progression, distant progression, and any (of the 3 categories) progression. We will construct 95% confidence intervals around these proportions. Those patients for whom we are unable to determine progression status at 1 and 2 years (e.g., because they do not return for the necessary scans, or because they die without evidence of progression) will be left out of these analyses. We will evaluate PFS and OS first using the Kaplan-Meier lifetable method, and will estimate median survival and corresponding 95% CIs; we will also explore simple Cox proportional hazards models of each of these survival outcomes, to examine the predictive influence of variables such as age, gender, ECOG performance status, stage at diagnosis, PTV 7000+6750 volume, and PTV 5750 volume. Patients who are lost to follow-up will be censored at that time in these analyses.

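### The follow-up adverse event form (Appendix G) looks back only 30 days, although visits are 3 months apart and toxicity is reported over 25 months

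*Combined protocol and SAP*

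**What the plan says.** Section 5.2.1 has toxicity graded by CTCAE version 5.0 "one month following completion of therapy and then every 3 months thereafter until 25 months from completion of radiation therapy". The table in section 6.1 agrees. After the 1-month visit, its last column reads "Every 3 months after 1 month post-RT scan until 25 months after RT". The adverse event row carries footnote f, which says "f See Appendices F and G". A further footnote to the same table says of follow-up imaging and clinic time points that "a flexibility window of +/- 8 weeks is allowed".

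Appendix F is a log with CTCAE term, grade, start date and end date. It sets no look-back period. Appendix G gives the instruction "Complete this form to follow-up with patients for adverse events" and then asks "Did the subject have any adverse events in the last 30 days". It has no field for the visit at which it is completed. Its last item is "Did the subject complete the full course of SBRT and take the study drug".

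Section 11.2.1 analyses toxicity as the proportion of patients with "any toxicity of grade 2 or higher over the 25 months", with a 95% confidence interval.

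**The concern.** The endpoint accumulates over the whole follow-up period, whereas the form's question reaches back about one third of the way to the previous visit. An event that begins after one visit and has resolved more than 30 days before the next is a correct 'no' on Appendix G.

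The first gap falls at an awkward time. Section 9.1.4 describes radiation pneumonitis as arising weeks to months after treatment. An episode that is treated and settles between about day 30 and day 92 lies outside both the 1-month and the 4-month questions. Acute oesophagitis is a weaker example. Section 9.1.2 places it soon after radiotherapy, where the weekly on-treatment checks and the 1-month visit should see much of it.

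Toxicity is the first secondary objective (section 2.2.1), and section 1.0 presents the study as one of efficacy and safety. Under-recording would make the regimen look safer than it was. The error could not run the other way.

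**Working it through.** The documents give no coverage figure to reproduce, so this is direct arithmetic on their schedule.

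**Inputs**
- Look-back: 30 days (Appendix G).
- Visits: month 1, then every 3 months to month 25 (sections 5.2.1 and 6.1). These are months 1, 4, 7, 10, 13, 16, 19, 22 and 25, or 9 visits. Check: 1 + 8 × 3 = 25.
- Visit window: ± 8 weeks = ± 56 days (section 6.1).
- Month length: 365.25 / 12 = 30.44 days (my convention).
- Assumptions: Appendix G is completed at all nine visits, its question is taken literally, and the 25 months run from the end of radiotherapy.

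**Share of one 3-month interval covered by the question**
- Interval = 3 × 30.44 = 91.3 days.
- Covered = 30 / 91.3 = 32.9%.
- Not covered = 61.3 days, or 67.1%.

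**Share of all follow-up**
- Total = 25 × 30.44 = 761 days.
- Covered, at most = 9 × 30 = 270 days, or 270 / 761 = 35.5%.
- Not covered = 491 days, or 64.5%.
- The first month is almost fully covered by the 1-month visit, so the gap lies in months 1 to 25: 8 × 30 = 240 of 730.5 days covered, and 67.1% not covered.

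**Where the first gap lies**
- First visit at day 30.4; second at 4 × 30.44 = day 121.8.
- The second look-back starts at 121.8 − 30 = day 91.8.
- Not covered: about day 30 to day 92.

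**Effect of the visit window on one interval**
- Later visit 56 days early: 91.3 − 56 = 35.3 days; not covered (35.3 − 30) / 35.3 = 15%.
- Later visit 56 days late: 91.3 + 56 = 147.3 days; not covered 117.3 / 147.3 = 80%.
- Earlier visit early and later visit late: 91.3 + 112 = 203.3 days; not covered 173.3 / 203.3 = 85%.

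The window can therefore narrow the gap as well as widen it.

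**With the question reworded**
A question about the time since the last visit (since the end of radiotherapy at the first) would cover all 761 days for a patient who attends as scheduled.

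**From days to the endpoint**
These are shares of time, not of events or patients. Section 11.2.1 counts a patient once for any grade 2 or higher toxicity, so a missed event changes the result only if that patient has no other recorded event of that grade. Converting days to bias would need event timing, duration, clustering within patients and the yield of the other sources. The documents give none of these. For scale only: with all 30 patients of section 11.3 in the denominator, each patient wrongly counted as event-free lowers the proportion by 1/30 = 3.3 percentage points.

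**The case against.** A reader might infer that about two thirds of follow-up time goes unasked about in the trial as a whole, or that about 65% of short events are lost. The documents do not support either reading.

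- Footnote f names both forms, and the Appendix F log has start and end dates with no look-back limit.
- Section 5.2.1 requires CTCAE evaluation every 3 months without restricting it to the preceding 30 days.
- Section 6.1 schedules a medical history and physical examination at every follow-up visit. Section 9.1.4 calls for systemic steroids in more significant pneumonitis, which a history could be expected to reveal.
- The procedure in Appendix D requires every adverse event to be entered in the trial system.
- An event lasting weeks may overlap a look-back or still be present at the visit.

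It is also not stated that Appendix G is completed at every 3-month visit. Footnote f applies to a row that includes visits before and during radiotherapy, where a question about completing the course makes no sense. The 30 days match the minimum monitoring period in section 6.4 and the reporting window in Appendix D, so the form may have been meant for a single use after treatment. Section 10.0 lists a post-washout follow-up form, but does not say whether that is Appendix G.

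Most of this stands. It rules out any claim about how many events are lost, and it makes the coverage figure conditional on how the form is used. It does not remove the mismatch. Appendix F stores what someone has elicited and does not itself ask anything; its header is organised by cycle. The rule to enter all events applies only once an event is known. The concomitant medication form is for use before treatment only, so it would not show a later course of steroids. No form in the documents asks about the whole interval since the last visit. If Appendix G is for one use only, the plan should say so, and the later visits would then have no adverse event question on any form.

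**Conclusion.** The point holds in a limited form. Appendix G is one of the two forms named for adverse event evaluation, and its 30-day question does not fit 3-month visits or a 25-month endpoint. If it is used at each follow-up visit and taken literally, it covers at most about 270 of 761 days, or about 33% of each 3-month interval. Resolved grade 2 or higher events between look-backs could be missed where staff rely on that question alone.

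Any loss pushes the section 11.2.1 proportion downward. Its size cannot be estimated from the documents, and it could be nil if the log and the visit history work well. The 64.5% of days not covered should not be read as a share of events lost or as a bias in the endpoint.

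The item on SBRT and a study drug is a template error, since this trial gives 25-fraction radiotherapy and no study drug. It has little consequence for the data because Appendix J records whether treatment was completed. Overall this is a cheap improvement, not a flaw that undermines the analysis.

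**What to change.** 1. Reword the Appendix G question to: *Any adverse events since the last study visit (since the end of radiotherapy at the first visit)?* Have the onset date, resolution date and grade of each event transferred to Appendix F.
2. State on the form and in footnote f that Appendix G is completed at every follow-up visit, and add a visit field.
3. As a minor clean-up, replace the SBRT and study-drug item with one on completion of protocol radiotherapy, consistent with Appendix J.

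The cost is a few lines on one form and one footnote, with no added visit or procedure. The one downside is that the recorded toxicity rate may rise slightly. Recall over 3 months is less exact than over 30 days, which is a further reason to ask for dates and check them against the medical record.
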